6.2.2 Instruction for initiation of a New Cycle

A new course of treatment may begin on the scheduled Day 1 of a new cycle if:

- The ANC is $\geq 1,000/\mu\text{L}$;
- The platelet count is $\geq 50,000/\mu\text{L}$;
- Any study drug-related allergic reaction/hypersensitivity or sinus bradycardia/other cardiac arrhythmia adverse event that may have occurred has resolved to \leq grade 1 severity;
- Any other study drug-related adverse event that may have occurred has resolved to \leq grade 2 severity.

If these conditions are not met on Day 1 of a new cycle, the subject will be evaluated weekly and a new cycle of the combination will not be initiated until the toxicity has resolved as described above. If lenalidomide dosing was halted during the previous cycle and was restarted with a one-level dose reduction without requiring an interruption for the remainder of the cycle, then that reduced dose level will be initiated on Day 1 of the new cycle.

If lenalidomide dosing was omitted for greater than 15 days of the previous cycle or if the new cycle is delayed more than 7 days due to toxicity noted on the scheduled Day 1, then the new cycle will be started with a one-level dose reduction.

Treatment compliance

Subjects will be asked to maintain a diary to record the drug administration.

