4. TREATMENT PLAN

4.1 Phase I

Three dose levels of lenalidomide (10 mg, 15 mg, 20 mg) will be evaluated with a fixed dose of obinutuzumab (1000mg) as outlined in Table 1. (obinutuzumab will be given in divided doses on cycle 1; 100mg IV on day 1, and 900mg IV on day 2, subsequent doses will be given over 1 day) Up to 18 patients may participate in the Phase I component of the study, depending on the level at which toxicity is observed. Subjects will be assigned to a dose level based on the order of study entry and toxicities seen in prior patients. The dose escalation process is described below. There will be no intra-patient dose escalation. DLT will be assessed during the first course of each cohort (28 days), and refers to a medically significant event which meets criteria using National Cancer Institute Common Terminology Criteria for Adverse Events (NCI CTCAE) version 4. (see section 2.3.2)

Table 1. Dose levels to be tested in phase I portion

Dose Level	Lenalidomide Dose (days 2-22 followed by 6 days of no therapy)	Obinutuzumab dose
-1	5 mg	1000mg IV
1	10 mg	
2	15 mg	
3	20 mg	

4. 2 Phase II

Additional pts will be enrolled into two cohorts at the recommended dose level (MTD) established in Phase I up to a maximum of 30 patients each in two independently enrolling cohorts.

Cohort A: 30 patients with relapsed/refractory follicular lymphoma

Cohort B: 30 patients follicular lymphoma, marginal zone lymphoma or SLL

[figure not shown]
4. 3 Treatment Schedule

Lenalidomide capsules will be taken orally daily each day on days 2 - 22, followed by 6 days of no therapy of each 28-day cycle. Obinutuzumab will be given by intravenous infusion on day 1,,2, 8, 15, and 22 of cycle one and on day 1 of each subsequent cycle up to 6 cycles. Patients who do not progress following 6 cycles and are deriving benefit from the combination in the opinion of the treating physician can receive further cycles of combination up to 12 cycles of lenalidomide therapy. (As long as the patient does not exhibit progression, the decision of how many cycles of combination therapy beyond 6 is at the discretion of the treating team and investigator).

Extended dosing of obinutuzumab will begin after combination therapy if patients demonstrate at least stable disease on response assessment. In the extended dosing schedule, obinutuzumab will be administered every 2 months, and in the absence of progression, will be dosed for maximum of 30 months (combination + maintenance).

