6.2 DOSE MODIFICATION: LENALIDOMIDE

Subjects will be evaluated for AEs at each visit with the NCI CTCAE v4.0, see below for full instruction on initiation of a new cycle of therapy and dose modifications during a cycle of therapy.

Table 6, 7 Lenalidomide dose adjustment steps

Table 6: LENALIDOMIDE Dose Adjustment Steps	
Starting Dose	MTD mg daily for 21 days every 28 days
Dose Level -1	MTD -5 mg daily for 21 days every 28 days
Dose Level -2	MTD -10 mg daily for 21 days every 28 days
Dose Level -3	MTD-15 mg daily for 21 days every 28 days

Table 7: LENALIDOMIDE Dose Adjustment Steps in SLL	
Starting Dose	MTD or max of 10 mg daily for 21 days every 28 days
Dose level +1	Starting dose +5 mg daily for 21 days every 28 days
Dose level +2	Starting dose +10mg daily for 21 days every 28 days
Dose level +3	Starting dose +15mg daily for 21 days every 28 days
Dose level -1	Starting dose -5 mg daily for 21 days every 28 days
Dose level -2	Starting dose -10 mg daily for 21 days every 28 days
Dose level -3	Starting dose -15mg daily for 21 days every 28 days

The minimum dose level is 15mg below MTD or 5mg daily for 21 days, (whichever is higher).

Patients who cannot tolerate or require dose reduction below 5mg daily lenalidomide will not receive further doses of lenalidomide.

If the patient is attaining clinical benefit in the opinion of the treating physician, and has attained at least a partial response, obinutuzumab dosing will continue per study design to a maximum of 21 doses.

The starting dose will be predefined during the phase I portion of the study based upon cohort (see Table 2). In the phase II portion of the study, the starting dose will be the maximum tolerated dose as defined by phase I portion.

6.2.1 INSTRUCTIONS FOR LENALIDOMIDE DOSE MODIFICATIONS OR INTERRUPTION DURING A CYCLE.

Table 8: Dose Modification for Lenalidomide		
NCI CTC Toxicity Grade	Day 2-14 of Cycle	≥Day 15 of Cycle
Grade 3 neutropenia associated with fever (temperature $\geq 38.5^{\circ} \text{C}$) or Grade 4 neutropenia	
 • Hold (interrupt dose). • Follow CBC weekly. • If neutropenia has resolved to \leq grade 2 restart at next lower dose level and continue the cycle until Day 21. 	
 • Omit lenalidomide for remainder of cycle 
If neutropenia is the only toxicity for which a dose reduction is required. G-CSF may be used and the dose maintained for the next cycle at the investigators discretion.

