Thrombocytopenia \geqGrade 3 (platelet count $< 50,000/\text{mm}^3$)	
 • Hold (interrupt dose). • Follow CBC weekly. • If thrombocytopenia resolves to \leq grade 2 restart at next lower dose level and continue the cycle until Day 21. 	
 • Omit lenalidomide for remainder of cycle
Erythema multiforme \geq Grade 3	
 • Discontinue lenalidomide study drug. 	
 • Discontinue lenalidomide study drug.

2013-0261 - Obinutuzumab Plus Lenalidomide in Low Grade Lymphoma

			Dose
Sinus bradycardia/ other cardiac arrhythmia Grade 2	
 Hold (interrupt) dose. Follow at least weekly. If the toxicity resolves to ≤ grade 1 prior to Day 21 restart at next lower dose level and continue the cycle until Day 21. 	
 Omit lenalidomide for the remainder of the cycle. 	
≥ Grade 3	
 Discontinue lenalidomide study drug. 	
 Discontinue lenalidomide study drug. 	
Allergic reaction or hypersensitivity Grade 2-3	
 Hold (interrupt) dose. Follow at least weekly. If the toxicity resolves to ≤ grade 1 prior to Day 21 restart at next lower dose level and continue the cycle until Day 21. 	
 Omit lenalidomide for the remainder of the cycle. 	
Grade 4	
 Discontinue lenalidomide study drug. 	
 Discontinue lenalidomide study drug 	
Venous thrombosis/embolism ≥ Grade 3	
 Hold (interrupt) dose and start anticoagulation; restart at investigator's discretion (maintain dose level). 	
 Omit lenalidomide for remainder of cycle. Anticoagulation measures as described in Concomitant therapy section below. 	
other non-hematologic toxicity assessed as Lenalidomide-related ≥ Grade 3	
 Hold (interrupt) dose. Follow at least weekly. If the toxicity resolves to ≤ grade 2 prior to Day 21 restart at next lower dose level and continue the cycle until Day 21. 	
 Omit lenalidomide for remainder of cycle. Initiate appropriate supportive care, restart lenalidomide next cycle (decrease by one dose level) 	

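### Section 6.2.2, Table 8 and the rash table do not give one consistent next-cycle lenalidomide dose after a toxicity hold, and for some mid-cycle holds the slower-recovering patient can restart one level higher.

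*Combined protocol and SAP*

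**What the plan says.** Section 4.3 sets the calendar: "Lenalidomide capsules will be taken orally daily each day on days 2 - 22", then 6 days off, in a 28-day cycle. Section 6.2.1 (Table 8 and the rash table) governs holds within a cycle. Section 6.2.2 governs the start of the next one.

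- **Table 8, onset Days 2–14.** For neutropenia and thrombocytopenia, the drug is held and blood counts are followed weekly. On recovery the instruction is "restart at next lower dose level and continue the cycle until Day 21". The rows for grade 2 arrhythmia, grade 2–3 allergic reaction and other non-hematologic toxicity have the same pattern. The thrombosis row instead keeps the dose level on restart.
- **Table 8, onset Day 15 or later.** The drug is omitted for the rest of the cycle. The neutropenia cell refers to a required dose reduction and adds "G-CSF may be used and the dose maintained for the next cycle at the investigators discretion". The thrombocytopenia, grade 2 arrhythmia and grade 2–3 allergic reaction cells give no next-cycle dose. The other non-hematologic cell orders a one-level reduction.
- **Thyroid row and grade 3 rash.** Both columns order a one-level reduction in the next cycle, with no day count.
- **Section 6.2.2.** The carry-forward rule covers a drug that was halted and restarted one level lower "without requiring an interruption for the remainder of the cycle". For such a patient the instruction is "then that reduced dose level will be initiated on Day 1 of the new cycle". Otherwise a one-level reduction follows under either of two conditions. The first counts missed drug: "If lenalidomide dosing was omitted for greater than 15 days of the previous cycle". The second concerns a late start and applies "if the new cycle is delayed more than 7 days due to toxicity noted on the scheduled Day 1".

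No text says which section prevails, or whether the 15 days are doses or calendar days.

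**The concern.** The carry-forward sentence in 6.2.2 covers only patients who restarted within the cycle. A patient too slow to restart must meet the 15-day or the 7-day condition instead. With 21 dosing days in a cycle, a mid-cycle hold may be too late for more than 15 days to be omitted. The rule could then reduce the patient who recovered quickly and leave the slower one unreduced. If Table 8 and 6.2.2 also differ, the next dose depends on which text a site follows.

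These texts govern re-exposure after grade 4 or febrile grade 3 neutropenia and after grade 3 or higher thrombocytopenia. Section 1.3.1 names prolonged neutropenia as the dose-limiting toxicity of lenalidomide with rituximab, so slow marrow recovery is foreseeable. Safety is a phase II primary objective, and inconsistent re-dosing would make the toxicity tables harder to interpret.

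**Working it through.** **Inputs.** Dosing on Days 2–22 of a 28-day cycle (4.3); Table 8 restarts running to Day 21 (6.2.1); triggers of more than 15 days omitted and more than 7 days' delay (6.2.2); one dose level = 5 mg (Table 6).

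**Days omitted.** For a hold that starts on Day h and is not resumed, days omitted = L − h + 1, where L is the last day counted. The protocol does not define L, so three readings are shown.

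| Count | L | Onset days that exceed 15 | Onset within Days 2–14 that does not (days omitted) | Most omitted if onset is Day 15 or later |
|---|---|---|---|---|
| Doses, per 4.3 | 22 | 2–7 | 8–14 (15 down to 9) | 22 − 15 + 1 = 8 |
| Doses, per Table 8 | 21 | 2–6 | 7–14 (15 down to 8) | 21 − 15 + 1 = 7 |
| Calendar days | 28 | 2–13 | 14 only (15) | 28 − 15 + 1 = 14 |

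**Two patients with grade 4 neutropenia on Day 10.**
- One has recovered at the weekly check on Day 17, restarts one level lower, and keeps that level next cycle.
- The other recovers on Day 25 and starts the next cycle on time. Omitted: 22 − 10 + 1 = 13 doses (12 if counted to Day 21). Neither 6.2.2 trigger is met.
- By calendar days, 28 − 10 + 1 = 19. The trigger fires and the second patient is reduced as well. This example therefore depends on the count.

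**An onset that does not depend on the count: Day 14.** A patient recovered by Day 21 can restart one level lower and carry that level forward. A patient who does not restart has omitted 9 doses, 8 doses or 15 calendar days, none of which exceeds 15. With a delay of 7 days or less, 6.2.2 orders no reduction.

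**How long toxicity can last without a 6.2.2 reduction.** The next cycle is due on Day 29. A 7-day delay, which does not trigger, gives Day 36. By dose count, a hold from Day 8 can last 36 − 8 = 28 days with neither trigger met. A patient recovered at the first weekly check is held for 7 days and is reduced.

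**Onset on Day 15 or later.** The most that can be omitted is 8 doses or 14 calendar days, so the 15-day trigger cannot fire on any reading. The reduction that the neutropenia cell presumes is imposed by 6.2.2 only after a delay of more than 7 days.

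**Thrombosis, onset Days 2–14.** Table 8 keeps the dose level. Section 6.2.2 lowers it once more than 15 days are omitted. If the drug is not resumed, that means onset on Days 2–7, 2–6 or 2–13 under the three counts. The two instructions cannot both be followed.

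**End of dosing.** Table 8 continues a restarted cycle to Day 21; Section 4.3 doses to Day 22.

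**Size.** One level is 5 mg. The MTD is not known in advance. Assuming it is one of the planned levels, 5 mg is 5/20 = 25%, 5/15 = 33% or 5/10 = 50% of it.

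**The case against.** **Section 6.2.2 does reduce some slow recoverers.** A reader might infer that it never does. It does so after a delay of more than 7 days, or after an unresumed hold that starts on Days 2–7 by dose count (Days 2–13 by calendar days). The inversion needs a mid-cycle hold, no restart in the cycle, and a delay of 7 days or less. This stands.

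**The higher restart comes from silence.** No sentence orders the full dose for the slow patient. The Days 2–14 neutropenia and thrombocytopenia cells name only the next lower level for restart. Unlike several other rows, they do not require recovery before Day 21. A site could extend that level to the next cycle, although the words about continuing the cycle point to a restart within it. So the text permits the higher dose but does not mandate it.

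**Most of the extra reductions are compatible.** The rash, thyroid and Day 15 or later other non-hematologic rows might be taken to contradict 6.2.2. But 6.2.2 lists cases that require a reduction and does not say that there are no others, so a site can follow both. They conflict only if 6.2.2 is read as exhaustive. The thrombosis row is different, because its instruction is the opposite one.

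**There are safeguards.** A new cycle needs ANC of at least 1,000/µL, platelets of at least 50,000/µL and resolution of other drug-related toxicity to stated grades. Section 6.1.6 allows discretionary holds. These limit the harm but do not say what dose to give.

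**Conclusion.** The point holds as a defect of consistency and completeness. By dose count to Day 22, the inversion covers onset on Days 8–14, which is 7 of the 21 dosing days. It covers Days 7–14 if counted to Day 21, and Day 14 alone on calendar days. The difference is one level, 5 mg. It rests on reading 6.2.2 as written, with no reduction supplied from elsewhere.

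Four findings do not depend on how the 15 days are counted: the trigger cannot fire from Day 15 on; several Day 15 or later cells state no next-cycle dose, or presume one that 6.2.2 does not generally impose; the thrombosis row contradicts 6.2.2; and Day 21 does not match Day 22.

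Two larger readings are not supported. The 15-day trigger is out of reach by dose count for onset on 15 of 21 dosing days (Days 8–22), and a reader might take that as the extent of the inversion. But Days 15–22 have no restart within the cycle, so fast and slow recovery cannot be contrasted there. Nor does the problem reach MTD selection or the DLT stopping boundaries, because DLT is assessed in cycle 1 only. Any effect on later-cycle tolerability and dose intensity cannot be quantified from the documents.

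**What to change.** Reconcile Section 6.2.2, Table 8 and the rash table by amendment:

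- state which text governs where they differ, including the thrombosis row;
- define whether the 15 days are scheduled doses or calendar days, and the last day counted;
- state the next-cycle dose for holds that begin on Days 2–14 and are not resumed in the cycle, and for omissions from Day 15 on, including the cells that are now silent and the reduction presumed in the neutropenia cell;
- say whether the reductions listed in 6.2.2 are exhaustive;
- align Day 21 in Table 8 with dosing on Days 2–22.

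Which dose or rule applies is for the sponsor to decide. The cost is amendment wording, with no added visits or patients; some current practice may change.

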6.3 CONCOMITANT THERAPY

Anti-cancer therapies, including chemotherapy, chemoimmunotherapy, radiation, thalidomide, or any other investigational agents is not permitted while subjects are receiving study drug during the treatment phase of the study.

Patients can receive sargramostim (G-CSF) as treatment for grade 3 or greater neutropenia at the treating physicians discretion. Prophylactic growth factor is not permitted.

It is recommended that patients who are at high risk for a initial or recurrent thromboembolic event (high risk is defined as history of a thromboembolic event and/or taking a concomitant medication associated with an increased risk for a thromboembolic event and/or a known hypercoagulable state regardless of thromboembolic history) receive prophylactic aspirin (70 – 325 mg) daily unless contraindicated. If aspirin is contraindicated, use of low molecular weight heparin or warfarin (or equivalent Vitamin K antagonist) to keep the international normalized ratio (INR) in the range of 2-3, or use of other anti-thrombotic therapy according to hospital guidelines, or physician preference, is acceptable. However, the choice of anticoagulant for prophylaxis for VTE relies upon the investigator's discretion and should be tailored to the subject's individual risk/benefit profile by taking into account the individual thrombotic risk (e.g., history of venous thrombosis), bleeding risk, and the quality of compliance with antithrombotic treatment.

6.4 DISCONTINUATION OF STUDY TREATMENT

Follow-Up

Subjects who discontinue treatment, will be followed for a minimum of 6 months. Patients who die or withdraw consent will not be followed beyond the date of the death or withdrawal of consent. Patients who start alternative therapy will not be followed beyond initiation of next line therapy except for survival. All other patients that remain on study (ie completion of therapy, or drug interruption due to toxicity) will be followed with tumor lesion assessments, imaging, and survival per the schedule of assessments, Section 2.1. Subjects will undergo a safety assessment approximately 28 days post the last dose of study drug. In addition,

off study evaluations, such as recording subsequent therapy, per the Schedule of Assessments will be done. Following completion of chemotherapy, patients will be evaluated every 3 months for one year, then every 6 months for a total of 2 years following completion of therapy with CT of neck, thorax, abdomen and pelvis and other studies as recommended by the treating physician.

7. CRITERIA FOR SUBJECT DISCONTINUATION

7.1 OBINUTUZUMAB-SPECIFIC CRITERIA

Subjects who meet the following criteria should be discontinued from the study:

- Active HBV infection or hepatitis
- Severe or life-threatening anaphylaxis or hypersensitivity reaction

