6.1.1 MANAGEMENT OF INFUSION-RELATED REACTIONS AND ANAPHYLAXIS

Medications (including epinephrine for subcutaneous injections, corticosteroids, diphenhydramine hydrochloride for IV injection) and resuscitation equipment should be available for immediate use at point of infusion. Management of infusion-related symptoms for obinutuzumab is summarized in Table 4. In the event of a life-threatening IRR (which may include pulmonary or cardiac events) or an IgE-mediated anaphylactic reaction, obinutuzumab should be discontinued and no additional drug should be administered. Patients who experience any of these reactions should receive aggressive symptomatic treatment and will be discontinued from study treatment.

Patients who experience obinutuzumab -associated, infusion-related temperature elevations of $>38.5^{\circ}\text{C}$ or other minor infusion-related symptoms may be treated symptomatically with acetaminophen (≥ 500 mg) and/or H₁- and H₂-histamine–receptor antagonists (e.g., diphenhydramine hydrochloride, ranitidine). Serious infusion-related events, manifested by dyspnea, hypotension, wheezing, bronchospasm, tachycardia, reduced oxygen saturation, or respiratory distress, should be managed with additional supportive therapies (e.g., supplemental oxygen, β_2 -agonists, epinephrine, and/or corticosteroids) as clinically indicated according to standard clinical practice.

Table 4

Guidelines for Management of Infusion-Related Symptoms Related to Obinutuzumab

Infusion-Related Symptoms ^a	Guidance
Grade 4	
 Discontinue infusion immediately, treat symptoms aggressively, and do not resume treatment.
Grade 3	
 Hold infusion. Give supportive treatment.^b Upon symptom resolution, may resume infusion rate escalation at the investigator's discretion.^c If the same adverse event recurs with the same severity, treatment must be permanently discontinued.
Grade 1–2	
 Slow or hold infusion. Give supportive treatment.^b Upon symptom resolution, may resume infusion rate escalation at the investigator's discretion.^c

^a Refer to National Cancer Institute Common Terminology Criteria for Adverse Events, Version 4.0 for the grading of symptoms. This table does not refer to management of immunoglobulin E-mediated allergic reactions, which should be managed as directed in Section 6.1.1.

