7.2 GENERAL CRITERIA

- Inability of subject to comply with study requirements
- Determination by the investigator that it is no longer safe for the subject to continue therapy

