12.2.1 ADVERSE EVENT REPORTING PERIOD

The study period during which all AEs and SAEs must be reported begins after the first protocol intervention, and ends 30 days following the last administration of study treatment or study discontinuation/termination, whichever is earlier. After this period, investigators should only report SAEs that are attributed to prior study treatment.

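### Section 7.1 takes patients with certain severe reactions off the study, while 6.1.1, 6.4 and 9.3 take them off treatment and keep following them; read literally, 7.1 and 12.2.1 end their follow-up early

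*Combined protocol and SAP*

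**What the plan says.** **Leaving the study.** Section 7.1 opens with "Subjects who meet the following criteria should be discontinued from the study". Its two criteria are active hepatitis B infection or hepatitis, and "Severe or life-threatening anaphylaxis or hypersensitivity reaction". Section 7.2, under the same Section 7 heading, has no lead-in. One of its two entries is "Determination by the investigator that it is no longer safe for the subject to continue therapy".

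**Leaving treatment.** For a life-threatening infusion reaction or IgE-mediated anaphylaxis, Section 6.1.1 says: "Patients who experience any of these reactions should receive aggressive symptomatic treatment and will be discontinued from study treatment". Section 8 is headed as criteria for study discontinuation, but its text stops study drug.

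**Follow-up.** Section 6.4 says "Subjects who discontinue treatment, will be followed for a minimum of 6 months", and later: "All other patients that remain on study (ie completion of therapy, or drug interruption due to toxicity) will be followed with tumor lesion assessments, imaging", with survival added. Section 9.3 sets the same 6-month minimum for every reason for stopping except completion of therapy. Both sections call for a safety assessment about 28 days after the last dose.

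**Safety window.** Under Section 12.2.1, reporting of AEs and SAEs "ends 30 days following the last administration of study treatment or study discontinuation/termination, whichever is earlier"; after that, only SAEs attributed to prior treatment are reported. Section 12.1.2 captures SAEs to 30 days after the last dose unless consent is withdrawn.

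**Analysis.** TTP and PFS are secondary objectives (2.2.2). Section 11.2 estimates PFS and OS by Kaplan-Meier and gives no censoring rule. Safety is a phase II primary objective (2.2.1).

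**The concern.** The same patient can be off the study under one section and in follow-up under another, and site staff have no rule for choosing. If 7.1 is followed, observation ends because of a severe reaction. Patients who leave for that reason may differ in prognosis from those who stay, and Kaplan-Meier assumes that censored patients do not. The effect would fall on PFS, TTP and OS. If 12.2.1 is also read in its narrower sense, AE collection closes in the very patients whose safety course is of most interest.

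**Working it through.** **1. The sections side by side**

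| Section | Who | What ends |
|---|---|---|
| 7.1 | Active hepatitis B infection or hepatitis; severe or life-threatening anaphylaxis or hypersensitivity | The study |
| 7.2 | Non-compliance; therapy judged unsafe | Not stated |
| 6.1.1 | Life-threatening infusion reaction; IgE-mediated anaphylaxis | Study treatment |
| 8 | Adverse events that rule out more study drug | Study drug |
| 6.4, 9.3 | Patients who stop treatment | Treatment; at least 6 months of follow-up required |

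A patient with life-threatening anaphylaxis falls under both 7.1 and 6.1.1 and gets two different dispositions. Section 6.4 does not settle it. Its tumour and survival follow-up applies to patients who remain on study, and a literal reader of 7.1 would say that this patient does not.

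**2. The two readings of 12.2.1**

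- Reading (a): 30 days are counted from the earlier of last dose and study discontinuation. A patient who leaves the study on or after the last dose keeps the full 30 days.
- Reading (b): the window closes at the earlier of two dates, namely 30 days after the last dose, or the date of study discontinuation. A patient removed under 7.1 on the day of the reaction then has no window left, against 30 days for SAEs in 12.1.2.

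The sentence allows both. Only (b) conflicts with 12.1.2.

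**3. What a lost patient costs**

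The plan gives no figure for this, so there is none to reproduce. Let *d* of the 30 patients in a phase II cohort leave before progression, and let *f* be the progression-free proportion at a fixed time among the rest.

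- Worst case (all lost patients progressed): *f*(30 − *d*)/30
- Best case (none progressed): [*f*(30 − *d*) + *d*]/30
- Width: *d*/30, whatever *f* is

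With *f* = 0.60 as an assumption for illustration:

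| *d* | Worst | Best | Width |
|---|---|---|---|
| 1 | 58% | 61% | 3 points |
| 3 | 54% | 64% | 10 points |
| 6 | 48% | 68% | 20 points |
| 9 | 42% | 72% | 30 points |

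These are outer bounds: Kaplan-Meier uses the time observed before loss, and the true outcomes would rarely all go one way.

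**4. How large *d* might be**

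The documents give no rate for the 7.1 events on this regimen. Two loose upper markers exist:

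- Grade 3/4 infusion reactions occurred in 11% of the obinutuzumab arm of the randomised monotherapy study (Section 1.2.3): 0.11 × 30 = 3.3 patients. Not all would meet 7.1.
- The 30% ceiling on cycle-1 DLT in Section 11.1.2 gives 0.30 × 30 = 9. It counts many toxicities that are not 7.1 criteria.

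Neither is an estimate of *d*.

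**The case against.** **The protocol uses study and treatment discontinuation loosely.** Section 8 shows this, and the schedule in Section 2.1 moves from discontinuation of study drug to a follow-up phase. Loss to follow-up is therefore one reading of 7.1, not its certain effect. This stands, but it also shows why the wording needs settling.

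**Follow-up is already required.** The 6-month minimum in 6.4 and 9.3 makes no exception for toxicity. This stands too, and it is half of the contradiction: 7.1 tells the site otherwise.

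**Stronger readings that a reader might infer, and that the documents do not support:**

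- *Every patient judged unsafe to continue leaves the study.* The words about leaving the study introduce only the two 7.1 criteria. Carrying them into 7.2 is a natural inference from the shared heading, but 7.2 speaks of continuing therapy.
- *Patients who stop for toxicity are lost in general.* Most toxicity rules in Section 6 hold or stop a drug and leave participation untouched.
- *Late safety is lost.* Sections 12.1.2, 12.2.1 and the post-study paragraph of 12.3.2 keep treatment-attributed SAEs reportable after the window or after participation ends.
- *The 5 of 28 patients (18%) withdrawn from the fludarabine-cyclophosphamide combination for neutropenia (3), rash (1) and infection (1) measure the loss.* None of these reasons, as stated, is a 7.1 criterion, and the regimen differs. Scaling that rate to 60 patients is unsupported.

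**The decision rule is untouched.** Phase II monitoring in 11.1.2 uses response after 6 cycles and cycle-1 DLT. PFS and TTP are secondary, and OS is analysed without being a listed objective. This limits the weight of the point.

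**Conclusion.** The contradiction between 7.1 and Sections 6.1.1, 6.4 and 9.3 is real, and 7.2 is silent where it should not be. If 7.1 is applied literally, tumour and survival observation ends at a toxicity-related time, with a risk of informative censoring that 11.2 does not address. If 12.2.1 is read in sense (b), ordinary AEs and unattributed SAEs in the 30 days after the last dose may go uncollected in the same patients.

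The number affected cannot be derived from the documents. It is probably small, because the 7.1 criteria are narrow and Section 3.2 already excludes any history of hepatitis B and prior severe reactions to monoclonal antibodies. The size that can be stated is per patient: 1/30, or about 3 percentage points of best-to-worst range. This assumes a cohort of 30 and loss before progression with no later information. The point merits correction but does not threaten the phase II decision.

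**What to change.** - **Sections 6.1.1, 6.4, 7.1, 7.2 and 9.3:** reconcile them so that meeting a Section 7 criterion ends study treatment but not study follow-up. Tumour, survival and safety follow-up then continue under 6.4, 9.3 and Section 2.1 unless the patient dies, withdraws consent or, for tumour assessments only, starts next-line therapy. The same edit should settle survival follow-up after next-line therapy, which 6.4 keeps and 9.3 ends.
- **Section 12.2.1:** end AE reporting 30 days after the last dose of the last study drug received. Delete study discontinuation as an earlier end, except for withdrawal of consent. The wording must name the last drug received, because lenalidomide ends after 6 to 12 cycles while obinutuzumab can run to 30 months in total. A rule tied to either drug could close AE collection during maintenance.
- **Section 11.2:** state the censoring rule for PFS and TTP.

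No change is proposed to when drug is stopped. The cost is wording plus a few more scans and contacts; the visits are already in the schedule. Assessments missed under the literal reading could not be recovered later.
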